#### **9.1.5.2. Denervation Procedure**

The renal artery denervation procedure will be performed according to the supplied Symplicity Spyral catheter *IFU*, Symplicity G3 generator *User Manual* and associated training provided by Medtronic. Pre-treatment with both anxiolytic medications and analgesic medications, such as morphine sulfate or fentanyl (with additional doses timed with ablation treatments as appropriate) should be considered. Blood pressure, O2 saturation, and heart rate should be closely monitored both during the procedure and throughout the recovery phase from the conscious sedation administered.

The goal of the denervation procedure in this protocol is to ablate renal nerves where they are in close proximity to the vessel lumen by delivering RF energy in a helical pattern in the distal main renal artery and branch vessels coming off the main renal artery (first order branches).

[figure not shown]
The following are required:

- Placement of the catheter in each accessible renal artery branch vessel coming off the main renal artery to achieve  $\leq 4$  lesions in a helical pattern and
- Placement of the catheter in the most distal, treatable portion of the main renal and/or renal accessory arteries to achieve  $\leq 4$  lesions in a helical pattern

Note 1: Initial placement of the Symplicity Spyral catheter should not extend into the renal parenchyma as identified on fluoroscopic imaging.

Note 2: Depending on anatomy, branch and main renal artery should be treated with the goal of applying 4 ablations in each location.

Note 3: Uncommon subject anatomy variations may be treated per investigators discretion in accordance with protocol guidelines and procedural training.

**Figure 7: Schematic representation of positioning of Symplicity Spyral catheter.**

Blue dots represent the required placement of the Symplicity Spyral catheter in eligible arteries for an example anatomy. More information and training will be provided as part of the procedural training.

Upon completion of the denervation procedure either manual compression or commercialized closure devices can be used to achieve hemostasis at the puncture site. As per usual clinical practice, consider use of short acting anti-hypertensive medications for blood pressure control in the cath lab and prior to removing arterial access. Strict adherence to anticoagulation parameters prior to sheath withdrawal following either hospital protocol or standard of care practices are strongly recommended.

#### ***9.1.5.3. Post-procedure data collection requirements***

A copy of the renal angiogram cine procedure will be submitted to the angiographic core laboratory. Sedation type, procedure information, fluoroscopy time and contrast dye amount will be collected.

Symplicity G3 generator data will be downloaded by and submitted to Medtronic.

#### ***9.1.5.4. Post-procedure care***

All subjects will be hospitalized overnight following the renal angiogram and procedure and standard-of-care post-intervention monitoring procedures will be followed.

Prior to discharge, the research staff will collect blood samples, assess for adverse events, and review study requirements with the subject to help ensure compliance with the follow-up schedule. An office blood pressure will also be obtained by study personnel. Various contact details (including telephone numbers and email address) should be obtained from the participant (not supplied to the sponsor) to ensure the ability to contact the subject at the required follow-up times (e.g., home, work, cell, and primary physician).

Subjects shall be prescribed a minimum of 75 mg aspirin for one month post-procedure. If the subject has a documented allergy to aspirin, at least 75 mg clopidogrel per day for one month post-procedure may be prescribed.

#### ***9.1.6. Follow -up Visits***

See **Table 3** for details on follow-up visit window and modality requirements for follow-up visits. See **Table 4** and **section 9.1.9** for escape subject requirements. Subjects will return for follow-up visits at 2 weeks, 1 month, 6 weeks, 8 weeks (non-escape only), 10 weeks, 3 months, 6 months, and 12 months post-procedure. Additionally, a 1 month and 4 month post-procedure in-office follow up is required for subjects with a systolic OBP >140 at the 3-month follow-up visit (see **section 9.1.10**).

Follow-up procedures for subjects treated are listed below and must be performed through 12 months follow up for each subject unless otherwise specified. After completion of the study required follow ups, the subjects will return to receiving standard of care follow up.

- **Clinical assessment** will be conducted at the 2 week, 1 and 3-months post-procedure follow-up visit to evaluate the subject's current medical condition. At 4, 6, and 12-months follow up an abbreviated clinical assessment of weight only is required.
- **Office blood pressure** measurements will be obtained in accordance with guidelines in **Appendix 16.5** at all follow-up visits.

- **Laboratory tests** are required at 1, 3, 6, and 12-month follow-up visits:
  - **Basic metabolic panel Chem-7 (blood)**: serum-creatinine, sodium, potassium, blood urea nitrogen (BUN) or urea, bicarbonate, chloride, and glucose. Bicarbonate will not be measured for subjects enrolled in Europe.
  - **eGFR** will be calculated from the serum-creatinine in the Chem-7 panel for eligibility criteria by using the 4 variable Modification of Diet in Renal Disease (MDRD) Formula.
- **Medication and adverse event reviews** will be completed at each follow-up visit to assess any changes in medication usage or medical condition:
  - Enrollment (consent) to 6-months follow up: all medications and all adverse events
  - After 6-months follow up to 12-months follow up: all medications and all serious adverse events
- **Renal artery imaging** will be performed at the 6-month follow-up visit to assess if a renal artery stenosis is suspected. A renal duplex ultrasound (DUS) will be obtained at 6-months follow up and submitted to the DUS Core Laboratory. If the DUS is determined to be nondiagnostic a repeat DUS, a MRA, CT or angiogram will be performed (repeat imaging is to be completed within 30 days after confirmation of non-diagnostic imaging). If evidence of a clinically significant stenosis is indicated by the DUS or MRA/CT Core Laboratory, an angiogram must be obtained and submitted to the angiographic core laboratory.
  - If renal imaging is not obtained at the 6-month follow-up visit due to extenuating circumstances, renal imaging is required at the next scheduled study visit.
- **24-hour ABPM** will be conducted at the 3, 6, and 12-month follow-up visits post-procedure according to the guidelines in **Appendix 16.5**. A repeat ABPM will be required in the event of technical issues, failure to follow ABPM guidelines or if the minimum required number of daytime and nighttime readings is not obtained. If ABPM is repeated office blood pressure and drug testing (for 3-month follow up only) must be repeated on day the ABPM is applied.
  - Initiate medication re-Introduction for subjects with systolic OBP  $\geq 140$  mmHg at 3-month follow-up visit. Starting at the 3-month follow up after clinical assessment and a valid ABPM are completed.
- **Mortality assessment** will be completed by the investigational site when a subject cannot be reached after each of the protocol required follow-up visits.
- **Drug testing** (urine/blood) to ensure medications are no longer present in the subject's system. A urine sample will be collected, preferably using the subject's first morning urine. A blood sample will be collected at the time of the visit. Drug testing samples collected for subjects that screen fail after obtaining the sample, must not be sent to the core lab for analysis.

Alternative methods of data collection may be necessary in the case of extenuating circumstances, such as a global pandemic, when subjects are prohibited from coming into the office for required assessments. For all assessments completed via alternative methods in these circumstances, sites are not required to enter a protocol deviation for missing, and/or alternative data collection. Data unable to be collected remotely or via an alternative method should be collected at the next possible in-person visit. In the event a subject is unable to return for an in-office follow-up visit, the alternative methods of obtaining follow-up assessments are listed below:

In-home visit by trained and delegated site personnel or designee, for example, home health care personnel. The following assessments may not be completed with an in-home visit:

- **Renal artery imaging:**
  - Make every effort to schedule in-person renal artery imaging as soon as possible.
  - When possible, the subjects may be referred to a local imaging center for assessment. Local imaging technicians would require study training and delegation prior to assessment.

Virtual visit, inclusive of video with study subject, or a phone visit.

The following assessments may **not** be completed with a virtual visit or a phone visit:

- **Clinical assessment:** limited review to be completed per physician discretion.
- **Laboratory tests:**
  - When possible, the subject should be referred to a local laboratory to collect samples. Laboratory kits to be provided to subjects in advance of the visit by study site.
- **Renal artery imaging:**
  - Make every effort to schedule in-person renal artery imaging as soon as possible.
  - When possible, the subjects could be referred to a local imaging center for assessment. Local imaging technicians would require study training and delegation prior to assessment.
- **Office blood pressure and ABPM** units to be provided to the subjects in advance of the visit by the study site. Measurements collected by the subject may be collected and designated as subject-reported in the CRF.
  - Witnessed pill intake prior to ABPM, if applicable.
  - Documentation of pill intake will be assessed virtually or as confirmed verbally by subject.

### ***9.1.7. Unscheduled Follow-up Visits***

If subject returns to the institution between the protocol-required screening or follow-up visits for one of the following reasons: evaluation of subject for safety reasons, repeat procedures (serum creatinine blood draw, repeat renal imaging, or ABPM), or re-consenting, the visit will be treated as an unscheduled visit. The reason for the unscheduled visit, as well as any assessment data will be recorded on the Unscheduled Follow-up CRF and AE data on the Unscheduled visit CRF (if applicable). If the subject returns for another reason, documentation is not required.

### ***9.1.8. Confirmatory Blood Draws to Assess Renal Function***

Serum creatinine values will be assessed throughout the study. A second blood draw will be required to confirm a sustained change in renal function in the event of one of the following:

- >50% increase in serum creatinine from baseline (Screening Visit 2)
- eGFR <15 mL/min/1.73m^2 using the 4 variable MDRD calculation

The additional blood draw must be taken at least 21 days from the date of the event noted above and documented on an Unscheduled Follow-up CRF. In the event the second blood draw results in the same event (e.g., >50% increase in serum creatinine from baseline), an adverse event must be reported. If the event is a continuation of an already-identified sustained elevation that did not return to <50% of baseline value, another blood draw is not necessary.

### ***9.1.9. Anti-hypertensive medication escape criteria***

In the event a subject's office SBP  $\geq$ 180 mmHg, or there is a safety concern, from discharge up to and including the 3-month visit, the subject will be seen a second time within 72 hours for a repeat office BP. If the subject's office SBP remains  $\geq$ 180 mmHg, the subject will be put back on an antihypertensive medication regimen per the investigator's discretion. All efforts should be made to obtain an ABPM and Chem-7 panel, and urine and blood for antihypertensive drug testing, prior to the subject being put back on medications. If the subject already started medications, the subject and investigator should consider if it is safe to take the subject off medications for at least two weeks prior to the 3M visit in order to obtain the requirements at the 3-month visit to ensure endpoint data is collected. The subject will be exited from the off medications portion of the study and will be followed according to **Table 4**. If the subject's office SBP < 180 mmHg, the subject will continue to be followed per **Table 3**. At any time while the subject is not taking antihypertensive medications, either the subject or the investigator may restart antihypertensive medications if there is a safety concern and the subject will be followed according to **Table 4**. All blood pressures must be taken according to the guidelines in **Appendix 16.5** with the exception of needing to be completed by 10:30 am. Visits for monitoring the subject's BP for these purposes must be documented on the CRF.

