Medications prescribed 												X 		
Blood tests (Chem7) 			X		X		X				X		X	X
Serum or urine pregnancy test			X											
Drug testing			X								X			
Renal artery imaging– angiogram				X										
Renal artery imaging-DUS 													X	
Mortality assessment 						X	X	X	X	X	X	X	X	X
Medication and event review	X	X	X	X	X	X	X	X	X	X	X	X	X	X 

1: 4M follow-up is only required if 3M systolic OBP $\geq$ 140 mmHg, prescribe AH medications according to **section 9.1.9** if SBP  $\geq$  140 mmHg

2: If medically necessary, phone contact may be replaced with office visit. OBP (per **Appendix 16.5**) to be obtained for an office visit or following alternative methods of data collection as described in **section 9.1.6**.

3: Witnessed pill intake (if subject is taking AH medications), complete after OBP measurements

4: Bicarbonate will not be measured for subjects enrolled in Europe.

5: DUS required as first line imaging modality at 6M. Repeat DUS, MRA, CT or angiogram to be used if DUS is nondiagnostic. Renal angiography must be used if repeat DUS/CTA/MRA is nondiagnostic or stenosis >60-70% is suspected. If renal imaging is not captured at the 6M follow-up visit due to extenuating circumstances, renal imaging is required at the next scheduled study visit.

6: Mortality assessment will be completed by the investigational site when a subject cannot be reached after each of the protocol required follow-up visits

7: SAE only review required at 12M visit

8: Clinical assessment of weight only 8: Clinical assessment of weight only

**Table 4: Schedule of testing through 12 months for subjects with office SBP  $\geq 180$  mmHg (confirmed via 2 sets of measurements) or escape via investigator discretion during off-medication period post-procedure**

Required Assessments	Procedure		Post-Procedure						
	Procedure	DC	2Wk	1M	6Wk	10Wk	3M	6M	12M
Mode (O- in office, P-phone)			O	O	O	O	O	O	O
Window (M-month, Wk-week, d-days)	--	--	$\pm 3$ d	$\pm 7$ d	$\pm 3$ d	$\pm 3$ d	$\pm 14$ d	$\pm 14$ d	$\pm 30$ d
OBP per study guidelines		X	X	X	X	X	X	X	X
Renal artery imaging 								X 	
Mortality assessment 			X	X	X	X	X	X	X
Medication and event review		X	X	X	X	X	X	X	X 

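### Escape subjects may be asked to consider stopping drugs a second time for a 3-month BP that Table 4 only partly schedules and that, if SAP 7.1.3.1 controls, no 3-month analysis set uses

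*Protocol*

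**What the plan says.** **Escape and restart.** Under Protocol 9.1.9, a subject whose office SBP is confirmed at 180 mmHg or more, or for whom there is a safety concern, goes back on drugs. Before that, "All efforts should be made to obtain an ABPM and Chem-7 panel", together with urine and blood for drug testing. If drugs have already been restarted, investigator and subject are asked to "consider if it is safe to take the subject off medications for at least two weeks prior to the 3M visit". The stated purpose is "in order to obtain the requirements at the 3-month visit to ensure endpoint data is collected". The same paragraph takes the subject out of the off-medication part of the study and into Table 4.

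**Follow-up.** Protocol 9.1.6 says "See Table 4 and section 9.1.9 for escape subject requirements". Its listed procedures "must be performed through 12 months follow up for each subject unless otherwise specified". Laboratory tests "are required at 1, 3, 6, and 12-month follow-up visits", and 24-hour ABPM is placed at 3, 6 and 12 months. Protocol 9.1.8 adds: "Serum creatinine values will be assessed throughout the study". Table 4 and its synopsis copy, Table 2, have four rows only: office BP, renal artery imaging, mortality assessment, and medication and event review.

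**Analysis.** SAP 7.1.3.1 handles escapes in the ITT set by LOCF, limited to BP dated on or before the escape date and at least 30 days (criterion 2) or more than 30 days (criterion 3) after the procedure. Unscheduled readings count. SAP 7.1.3.3 removes escapes from the per-protocol set. SAP 7.1.3.2 is garbled but clearly means to remove them from the modified ITT set. SAP 7.3 imputes nothing.

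**The concern.** Protocol 9.1.9 gives one reason for the second withdrawal: endpoint data at 3 months. The people concerned have just shown a confirmed office SBP of 180 mmHg or more, or raised a safety concern, and Protocol 10.1 lists death, stroke and myocardial infarction among the risks of being off drugs. A repeat withdrawal in this group needs an analytic use. The SAP rule written for escapes appears to give it none, and the visit table for escapes does not schedule the ABPM that the withdrawal is meant to make interpretable.

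Two further matters follow from the same text. First, whether an escape subject has any 24-hour SBP value for the primary (ITT) comparison depends on a best-efforts ABPM before restart and on an escape date that is not defined. Second, a site working from Table 4 alone would draw no creatinine after escape, although a rise above 50% is a listed safety endpoint.

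**Working it through.** The plan attaches no figure to this point, so the check is of dates and table rows.

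**1. Can a post-withdrawal 3-month value pass the LOCF rule?** Let *d* be the escape date, *r* the restart day, *s* the day drugs are stopped again and *v* the 3-month visit. Whether the escape date means the first high reading, the confirming visit or the restart, *d* ≤ *r*. Also *s* > *r*, and 9.1.9 needs *v* ≥ *s* + 14.

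- Hence *v* ≥ *s* + 14 > *r* + 14 ≥ *d* + 14, so *v* > *d*.
- LOCF criterion 1 requires *v* ≤ *d*. No value can satisfy both.
- The visit window is days 76 to 104 (90 ± 14), so drugs must stop by day 62, 76 or 90 for a visit on day 76, 90 or 104. Running through escape days 1 to 89 and every visit day in the window gives 0 passing combinations.

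**2. The three 3-month sets.** ITT: excluded by criterion 1. Modified ITT: escapes removed, as intended. Per protocol: escapes removed. Sets that use the value: 0 of 3, if SAP 7.1.3.1 controls.

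**3. What LOCF leaves for 24-hour SBP.** Criteria 2 and 3 together admit days 31 to *d*; criterion 2 alone would admit days 30 to *d*. They differ on day 30 only, and an escape before day 30 has no eligible value under either. No ABPM is scheduled between the procedure and 3 months, so for an escape before the 3-month visit the only candidate is the pre-restart ABPM. SAP Appendix III dates an ABPM by its start. One begun on the day of the confirming visit passes if the escape date is that visit or the restart. One begun on a later day, but before restart, passes only if the escape date is the restart date.

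**4. The 3-month column, Table 3 against Table 4.**

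| Item at 3M | Table 3 | Table 4 |
|---|---|---|
| Office BP | yes | yes |
| 24-hour ABPM | yes | no |
| Drug test | yes | no |
| Chem-7 | yes | no |

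So 9.1.9 asks for the 3-month requirements and, in the same paragraph, assigns a schedule that lacks three of them.

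**5. Chem-7 after discharge.** Table 3 has 4 draws (1, 3, 6 and 12 months) and Table 4 has 0. The draws missing after escape are 4 if escape comes before 1 month, 3 if between 1 and 3 months, and 2 if at 3 months with that draw already taken.

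**The case against.** **The withdrawal is a guarded fallback.** This stands. It follows an instruction to get the tests before restart, applies only if drugs have already been started, and is to be considered only if safe. Table 4 turns the 6- and 10-week contacts into office visits, and drugs may be restarted at any time for safety. A reader might infer that the protocol orders a second withdrawal; it does not.

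**Other texts might let the value in.** Protocol 13.2.1 states LOCF with no escape-date limit and defers to a table specifications document that is not among those supplied. SAP Appendices II and III, read alone, would pick up a scheduled 3-month value without excluding escapes. A flat statement that no analysis uses the value is therefore too strong. I take SAP 7.1.3.1 as controlling because it is the rule written for escape subjects.

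**Table 4 may be the stated exception.** Section 9.1.6 allows exceptions and points escapes to Table 4 and 9.1.9, and Table 4 is visibly a reduced schedule: it also drops the 6- and 12-month ABPMs and the clinical assessments. That reading is open. But Table 4's silence is not a reliable exemption, since it also omits Chem-7 at discharge, although Protocol 9.1.5.4 calls for blood samples then. I single out Chem-7 because it feeds a safety endpoint. Note too that 9.1.9 names Chem-7 only for before restart; at 3 months it comes in through the general 3-month requirements.

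**The day-30 mismatch is small.** Agreed: it affects one day. A reader might infer that many 1-month office readings are lost because they fall on or before day 30. That has little bearing, because unscheduled readings count and, for a BP escape after day 30, the confirming office reading normally qualifies.

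**Conclusion.** The point holds as a conflict between 9.1.9, Table 4 and SAP 7.1.3.1. If SAP 7.1.3.1 controls, a BP taken after a second withdrawal enters 0 of 3 three-month analysis sets, and an escape without a qualifying pre-restart ABPM after day 30 has no 24-hour SBP under the LOCF rule. The SAP does not say whether such a subject is then left out of the ITT analysis or takes an Appendix III value. Separately, Table 4 leaves 2 to 4 Chem-7 draws unscheduled per escape subject. The number affected is unknown because the documents give no escape rate; each such subject is 1/50 = 2% of the planned treated group.

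Two stronger conclusions are tempting and not supported. A reader might infer that dropping escapes overstates the mean fall in 24-hour SBP by some number of mmHg. That needs an escape rate, the share of escapes with no usable value, and their deficit in response, none of which the documents give. A reader might also infer that an untested subject would count as free of a creatinine event through the last-contact denominator in SAP 7.7.1. That algorithm is worded for events adjudicated by the CEC, and the SAP says the creatinine endpoint is not adjudicated. What remains is that creatinine may go unmeasured after escape at a site that follows Table 4 alone.

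**What to change.** Choose one of two options; the clinical choice is the sponsor's.

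- **A.** Delete the washout sentence from Protocol 9.1.9 and rely on the ABPM, Chem-7 and drug test taken before restart.
- **B.** Keep the sentence, add a 3-month ABPM and drug test to Tables 2 and 4 for subjects who complete the washout, and use that value in a named sensitivity analysis in the SAP.

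Under either option:

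- In SAP 7.1.3.1, define the escape date as the date drugs are restarted, so that the pre-restart ABPM qualifies.
- Use one day-30 cut-off in criteria 2 and 3, and say what happens to an escape with no eligible value.
- Add Chem-7 at 1, 3, 6 and 12 months to Tables 2 and 4, in line with Protocol 9.1.6.

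The cost is wording plus at most four blood draws per escape subject, which 9.1.6 arguably already requires. Option B adds one ABPM and one drug test per subject who completes the washout. No new visits are needed, because Table 4 already has office visits at 1, 3, 6 and 12 months.
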